7.2.1. Withdrawal of Consent

Participants who request to discontinue receipt of study intervention will remain in the study and must continue to be followed for protocol specified follow-up procedures. The only exception to this is when a participant specifically withdraws consent for any further contact with him or her or persons previously authorized by the participant to provide this information. Participants should notify the investigator in writing of the decision to withdraw consent from future follow-up, whenever possible. The withdrawal of consent

should be explained in detail in the medical records by the investigator, as to whether the withdrawal is only from further receipt of study intervention or also from study procedures and/or posttreatment study follow-up and entered on the appropriate eCRF page. In the event that vital status (whether the participant is alive or dead) is being measured, publicly available information should be used to determine vital status only as appropriately directed in accordance with local law.

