7.3. Lost to Follow-up

A participant will be considered lost to follow-up if he or she repeatedly fails to return for scheduled visits and is unable to be contacted by the study site.

The following actions must be taken if a participant fails to return to the clinic for a required study visit:

- The site must attempt to contact the participant and reschedule the missed visit as soon as possible and counsel the participant on the importance of maintaining the assigned visit schedule and ascertain whether or not the participant wishes to and/or should continue in the study.
- Before a participant is deemed lost to follow-up, the investigator or designee must make every effort to regain contact with the participant (where possible, 3 telephone calls and, if necessary, a certified letter to the participant's last known mailing address or local equivalent methods). These contact attempts should be documented in the participant's medical record.
- Should the participant continue to be unreachable, he/she will be considered to have withdrawn from the study.

All attempts to contact the participant and information received during contact attempts must be documented in the participant's medical record. In any circumstance, every effort should be made to document participant outcome, if possible. The investigator should enquire about the reason for withdrawal, request the participant to return for a final visit, if applicable, and follow up with the participant regarding any unresolved AEs.

If it is determined that the participant has died, the site will use permissible local methods to obtain the date and cause of death. If, after all attempts, the participant remains lost to follow-up, then the last-known-alive date as determined by the investigator should be reported and documented in the participant's medical records.

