Secondary: Time to recurrence of low-grade disease as assessed by investigator, defined as the time from randomization to the date of first documentation of recurrence of low-grade disease or death due to any cause.	
The treatment effect will be estimated using a Cox's Proportional Hazard model stratified by randomization strata to calculate the hazard ratio for time to recurrence of low-grade disease between each experimental arm and Arm C.
 
Time to recurrence of low-grade disease will be analyzed using Kaplan-Meier methods. Kaplan-Meier estimates (product-limit estimates) will be presented by treatment arm together with a summary of associated statistics including the median time to recurrence of low-grade disease with 2-sided 95% CIs. Time to recurrence of low-grade disease rates at various time points will be estimated with corresponding 2-sided 95% CIs. The CIs for the median will be calculated according to Brookmeyer and Crowley (1982) and the CIs for the survival function estimates at the time points will be derived using the log-log transformation according to Kalbfleisch and Prentice (2002) (with back transformation to a CI on the untransformed scale). ^{50,51} The estimate of the standard error will be computed using Greenwood's formula.
 
Time to recurrence of low-grade disease will be censored as defined in Table 3 for the primary analysis of EFS but with event being recurrence of low-grade disease or death due to any cause.

Endpoint	Statistical Analysis Methods
Secondary: Time to cystectomy, defined as time from randomization to cystectomy.	
The treatment effect will be estimated using a Cox's Proportional Hazard model stratified by randomization strata to calculate the hazard ratio for time to cystectomy between each experimental arm and Arm C.
 
Time to cystectomy will be analyzed using Kaplan-Meier methods. Kaplan-Meier estimates (product-limit estimates) and corresponding 2-sided 95% CIs will be presented. Participants without cystectomy will be censored at date last known not to have a cystectomy.

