
**Table 1. Summary of Major Changes in SAP Amendments**

Version	Version Date	Summary of Changes
		
summary of events. Removed text regarding central pathology and independent review of imaging scans.
 
Section 6.2.2.6 “Time to Recurrence of Low-Grade Disease” - added in text “according to the “Oncology Biopsy” CRF page” for how low-grade Ta disease will be determined. In Table 17, added in “adequate” for “No adequate baseline” and revised text to “EOS present OR all EOT disposition pages of all drugs in the treatment arm say participant will not continue into any”. Added the footnote “[b] EOS here refers to completion of follow-up disposition page.”
 
Section 6.2.2.7 “Disease specific survival” - in Table 18 updated lost to follow-up timing to 25 weeks from 24 weeks.
 
Section 6.2.2.8 “Time to cystectomy” - updated censoring to be “death date or last date known to be alive”. In Table 19, updated lost to follow-up timing to 25 weeks from 24 weeks.
 
Section 6.2.3 “Pharmacokinetic endpoints” - added the following test to the first bullet “will be excluded from”.
 
Section 6.2.6 “Endpoints for immunogenicity data of PF-06801591” - added in “Incidence may also be presented graphically and, if <math>\geq 10\%</math> in a treatment arm, immunogenicity titer data will also be summarized and box plots of PK concentrations by ADA and Nab status will be presented.” Updates were made to Table 20 for Nab negative subject row and removed reference to 2.00 and 0.602 titer in the first four rows. Included a range for EOT samples from 21 to 35 days of last PF-06801591 dose.
 
Section 6.5.1.1 “Demographics and baseline characteristics” - added in the words “and baseline” for clarification. Removed “<math><65</math>” in the second bullet under “Age categories”.
 
Section 6.5.1.3 “Disease characteristics” - included the T stage that is identified by biopsy according to worst stage: Ta, CIS, T1, T2, T3, T4
 
Section 6.5.1.4 “Prior anti-cancer therapies” - specified the CRF page name for “Prior Cancer Therapy”.
 
Section 6.5.2.1 “Participant disposition” - removed summary of number of participants entering a period but not that are treated. Added in number of participants entering each BCG period and number of participants ongoing in follow-up.
 
Section 6.5.3 “Study treatment compliance and exposure” - updated text regarding partial doses.
 
Section 6.5.3.4 “Dose delays” - removed the delay of 1-3 days in Cycles 1-3 and 1-7 days in Cycles 4-25 and categorized these as no delays to be consistent with protocol dosing window.
 
Section 6.5.4 “Concomitant medications and non-drug treatments” - the references to prior medications were removed.
 
Section 6.6.6 “Electrocardiogram” - removed text regarding ECG summaries and listings. Also removed referenced to QtcLogP and added that additional corrections may be performed.
 
Section 7.2.1 “Interim analysis for EFS” - deleted the word “vital”.
 
Section 8 “REFERENCES”- added reference #18.
 
Appendix 2 “List of Abbreviations” - removed QtcLogP reference Additional clarifications for consistency as needed were added.

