### 2.1. Modifications to the Analysis Plan Described in the Protocol

Changes	Protocol	SAP
Cohort A: Complete response as assessed by BICR	Specified	Removed
Cohort A: Duration of CR as assessed by BICR	Specified	Removed

The removal of the analysis of complete response (CR) and duration of CR (DoCR) by BICR described in the protocol is based on the infeasibility of these analyses without large amount of data imputations based on investigator assessment. As per protocol, on-study biopsy is not required at each disease assessment visit, therefore central pathology assessment of CR could not be performed at each visit, and independent oncology review of CR is not feasible.

In addition, to adhere to the requirements from the FDA with reference to independent evaluation of EFS events and CR, the following summaries were added:

- BICR oncology evaluation of investigator-assessed EFS events (Section 6.2.2.3).
- BICR biopsy evaluation of investigator-assessed CR (Section 6.2.2.5).

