### 6.2.2.10. Time to cystectomy (Cohort A only)

Time to cystectomy is defined as time from 'start date' to cystectomy. Participants without a cystectomy will be censored at death date or last date known to be alive.

The treatment effect will be estimated using a Cox's Proportional Hazard model stratified by randomization strata to calculate the hazard ratio for time to cystectomy between each experimental arm and Arm C.

Kaplan-Meier estimates (product-limit estimates) will be presented by treatment arm together with a summary of associated statistics including the median time to cystectomy with 2-sided 95% CIs. Time to cystectomy rates at 6, 12, 18, 24, 30, 36, 42, and 48 months will be estimated with corresponding 2-sided 95% CIs. The CIs for the median will be calculated according to Brookmeyer and Crowley (1982) and the CIs for the survival function estimates at specific time points will be derived using the log-log transformation according to Kalbfleisch and Prentice (2002) (with back transformation to a CI on the untransformed scale). The estimate of the standard error will be computed using Greenwood's formula. A Kaplan-Meier plot for time to cystectomy will be generated.

Reasons for censoring will be summarized according to the categories in Table 23 following the hierarchy shown.

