**Table 23. Time to Cystectomy Censoring Reasons and Hierarchy**

Hierarchy	Condition	Censoring Reason
1	No event and participant died	Death prior to event
2	No event and [withdrawal of consent date $\geq$ 'start date']	Withdrawal of consent
3	No event and [lost to follow-up in any disposition page OR data cut-off date – last contact date $>$ 365 days ]	Lost to follow-up
4	No event and none of the conditions in the prior hierarchy are met	Ongoing without an event

A listing for time to cystectomy will be provided.

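### Time to cystectomy: Kaplan-Meier rates to 48 months censor deaths with no cumulative incidence planned, and the SAP's censoring date departs from the protocol's without an entry in SAP 2.1

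*SAP*

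**What the plan says.** SAP 6.2.2.10 plans a stratified Cox model comparing each experimental arm with Arm C, and a Kaplan-Meier analysis by arm: "Time to cystectomy rates at 6, 12, 18, 24, 30, 36, 42, and 48 months will be estimated". On censoring it states: "Participants without a cystectomy will be censored at death date or last date known to be alive". In SAP Table 23 the first censoring condition is "No event and participant died".

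No cumulative incidence function is planned for this endpoint. The SAP uses competing-risk methods only conditionally. COVID-19 deaths are treated as competing events in EFS and OS if they exceed 10% of deaths (6.2.2.3, 6.2.2.4). A cumulative incidence curve is planned for CR if more than 5% of participants stop treatment for COVID-19 before responding (6.2.2.5).

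Protocol 9.4.1.1 has a different censoring rule: "Participants without cystectomy will be censored at date last known not to have a cystectomy". The SAP's rule appears in its version 3 history as an update to "death date or last date known to be alive". SAP 2.1, which lists departures from the protocol's analysis plan, has two rows. Both concern BICR analyses, and the last is "Cohort A: Duration of CR as assessed by BICR".

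**The concern.** Kaplan-Meier with deaths censored estimates what the cystectomy rate would be if nobody died. Its complement is therefore at least as large as the proportion of participants who actually have a cystectomy by that time. Table 23 counts the deaths but does not correct the rates.

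This matters because fewer cystectomies is part of the rationale for Cohort A (protocol 2.1.1), and a 48-month figure is easily read as a patient's chance of losing the bladder. The overstatement also grows with mortality. If the drug improves survival, the arms' reported rates are biased by different amounts.

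The censoring date works in the other direction. A date on which someone is known to be alive, or to have died, is not necessarily a date on which cystectomy status was known. Counting unascertained time as time at risk lowers the estimated rate.

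**Working it through.** **Reproducing the SAP's mortality input.** SAP 5.1.1 gives a hazard ratio of 0.472 for 5-year OS of 0.80 against 0.90. Under exponential survival, ln(0.90)/ln(0.80) = 0.4722, which agrees.

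**Death hazards.** With 1056 randomized 1:1:1, a two-arm comparison has 2 × 1056/3 = 704 participants. SAP 5.1.2 expects about 64 deaths per comparison at the EFS final analysis and about 100 at the OS final analysis. Mean follow-up is taken as 36 or 60 months after the last randomization, plus an assumed 8 to 14 months for the 22-month accrual. The hazard is −ln(1 − d/704)/follow-up:

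- d = 64, 44 to 50 months: 0.0022 to 0.0019 per month
- d = 100, 68 to 74 months: 0.0023 to 0.0021 per month

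The values 0.0020 and 0.0022 are used below.

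**Excess of 1 − KM over cumulative incidence.** For an assumed 48-month 1 − KM value p, the cystectomy hazard is hc = −ln(1 − p)/48. With death hazard hd, the cumulative incidence at 48 months is hc/(hc + hd) × [1 − exp(−48(hc + hd))].

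Worked case, p = 10% and hd = 0.0020:

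- hc = 0.10536/48 = 0.002195, and hc + hd = 0.004195
- 1 − exp(−0.20136) = 0.1824
- cumulative incidence = 0.5232 × 0.1824 = 9.54%, an excess of 0.46 points

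| Assumed 1 − KM at 48 months | Excess, hd = 0.0020 | Excess, hd = 0.0022 |
|---|---|---|
| 5% | 0.23 points | 0.25 points |
| 10% | 0.46 points | 0.50 points |
| 15% | 0.68 points | 0.74 points |
| 20% | 0.90 points | 0.98 points |

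In relative terms this is about 5% (for example 0.46/9.54).

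**Unequal bias between arms (illustration).** Under the SAP's OS alternative the death hazards are −ln(0.80)/60 = 0.00372 in Arm C and −ln(0.90)/60 = 0.00176 in Arm A. With equal cystectomy hazards and 1 − KM of 10.0% in both arms, cumulative incidence is 9.2% in Arm C and 9.6% in Arm A, a gap of about 0.4 points. At an assumed mean follow-up of 47 months these hazards imply 352 × (1 − e^(−0.00372 × 47)) + 352 × (1 − e^(−0.00176 × 47)) ≈ 56 + 28 = 84 deaths. That is more than the 64 projected, so the gap is illustrative only.

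**Scale.** The binomial 95% half-width for a 10% rate with 352 per arm is 1.96 × √(0.10 × 0.90/352) = 3.1 points.

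**Censoring date.** If scheduled contacts are kept, the interval from last contact to death is at most 12 weeks (survival calls) or 24 weeks (disease visits after year 2). One million participants were simulated with 36 to 58 months of follow-up, the interval uniform up to that limit, and p of 5, 10 and 20%. Censoring decedents at last contact rather than at death raises the 48-month rate by:

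| Longest interval | hd = 0.0020 | hd = 0.0037 |
|---|---|---|
| 12 weeks | 0.01 to 0.05 points | 0.02 to 0.09 points |
| 24 weeks | 0.03 to 0.10 points | 0.05 to 0.18 points |

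As a rough check, 64 deaths × 12 weeks is 64 × 84/30.4375 = 177 person-months, against about 704 × 44 = 30,976 in total, or 0.6%.

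**The case against.** The case for leaving the plan alone has real substance.

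- **The method is the protocol's own, and the comparison is sound.** Protocol 9.4.1.1 specifies Kaplan-Meier for this endpoint. The SAP does not say that the complement will be presented as a probability of cystectomy, and deaths are tabulated. A reader might infer that the treatment comparison is biased. It is not: censoring deaths in the Cox model gives a valid cause-specific hazard ratio. What stands is that the absolute rates are open to misreading and nothing planned corrects them.

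- **The change of censoring date is neither hidden nor forbidden.** A reader might infer an undisclosed departure. SAP section 2 says the SAP may modify the protocol's plans and reserves protocol amendments for major changes to the primary endpoint, and the version 3 history records this change. SAP 2.1 also omits the removal of death as an event in time to low-grade recurrence, so the omission is a general gap in that table. It remains a documentary gap.

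- **The rules diverge less than they first appear to.** The protocol allows other sources for vital status: "publicly available information should be used to determine vital status only as appropriately directed in accordance with local law" (7.2.1) and "the site will use permissible local methods to obtain the date and cause of death" (7.3). A reader might infer that such records add long stretches of unascertained time at risk. But SAP 5.3.3.1 limits last-contact dates to actual examinations of the participant and excludes disposition dates whose reason is loss to follow-up or death. If the last-alive date in 6.2.2.10 is that date, the rules differ mainly in two groups: deaths learned of after contact was lost, and contacts, such as a laboratory draw, that did not ascertain cystectomy.

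**Conclusion.** The point holds and is minor. The planned rates, read as complements, overstate the probability of cystectomy. The direction is certain whenever deaths occur before cystectomy. The size is about 0.2 to 1.0 points at 48 months, and it rests on constant hazards, the SAP's projected deaths, assumed mean follow-up and an assumed cystectomy rate of 5 to 20%. The 0.4-point imbalance between arms at a 10% rate is an illustration under an OS alternative with more deaths than the SAP projects. All of these are well inside the sampling error of a single arm's rate.

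The censoring-date difference is real. With scheduled contacts kept, it is worth at most about 0.2 points. Where a death is learned of after contact was lost, the documents do not allow it to be sized.

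The endpoint carries no alpha, the hazard ratio is unaffected, and no primary or key secondary conclusion changes. The reason to act is that the improvement is cheap and gives the quantity readers will want.

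**What to change.** In SAP 6.2.2.10:

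1. Add the Aalen-Johansen cumulative incidence of cystectomy by arm at the same time points to 48 months, with death before cystectomy counted as a competing event at the death date.
2. For participants alive without cystectomy, censor at the last completed visit or survival call at which subsequent anti-cancer therapy was ascertained. Alternatively, keep the SAP's date and list the change with a reason in SAP 2.1. This rule must not be applied to participants who died, because censoring them at their last contact would remove every competing event.
3. Keep the stratified Cox model and label its result a cause-specific hazard ratio.

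The ascertainment date would be derived from visit and call dates. The documents do not show a field recording that cystectomy was asked about and absent, so the sponsor should confirm that the derivation is workable; if it is not, the SAP 2.1 entry is the simpler choice.

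The cost is one extra table or figure, one or two SAP sentences or one line in SAP 2.1, and slightly shorter follow-up for a few participants.

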**Table 23. Time to Cystectomy Censoring Reasons and Hierarchy**

Hierarchy	Condition	Censoring Reason
1	No event and participant died	Death prior to event
2	No event and [withdrawal of consent date $\geq$ 'start date']	Withdrawal of consent
3	No event and [lost to follow-up in any disposition page OR data cut-off date – last contact date $>$ 365 days ]	Lost to follow-up
4	No event and none of the conditions in the prior hierarchy are met	Ongoing without an event

A listing for time to cystectomy will be provided.

### 6.2.3. Pharmacokinetic endpoints

The following pharmacokinetic analyses will be based on the PK analysis set by treatment arm for Cohort A.

$C_{trough}$  for PF-06801591 will be listed and summarized by treatment arm (Cohort A), cycle and study day relative to PF-06801591 dosing, and the summarized data will be plotted using box whisker plots to assess attainment of steady state. EOT concentrations will be excluded from  $C_{trough}$  data summaries and plots, unless the EOT visit coincides with a scheduled predose PF-06801591 sample (Cycles 1, 2, 4, 6, 8, 10, or 13 of Cohorts A) and has been collected prior to dosing, in which case it will be included in the summary statistics for the planned PK sample time.

Presentation of pharmacokinetic data will include:

- Descriptive statistics (n, mean, SD, %CV, median, minimum, maximum, geometric mean and its associated %CV, and 95% CI) of serum  $C_{trough}$ /predose concentrations will be presented in tabular form by treatment arm (Cohort A), cycle, and day. Zero values will

be excluded from the calculation of geometric means and its associated %CV. Data from samples collected at EOT will be presented in individual listings, but will be excluded from summary statistics, unless the EOT visit coincides with a scheduled PF-06801591 PK sample time.

- Box plots for  $C_{trough}$  for PF-06801591 will be generated by cycle for each treatment arm for Cohort A. The geometric mean and the median of the parameter in each treatment will be overlaid on the box plots. Data collected at EOT will be excluded, unless the EOT visit coincides with a scheduled PF-06801591 PK sample time.
- Individual serum  $C_{trough}$ /predose concentrations will be presented in spaghetti plots (linear scale) by treatment arm for Cohort A. Data collected at EOT will be excluded, unless the EOT visit coincides with a scheduled PF-06801591 PK sample time.

PK concentration data available for Cohort B1 and/or B2 will be provided in listings only.

#### **6.2.4. Population pharmacokinetic endpoints**

Pharmacokinetic and pharmacodynamic data from this study may be analyzed using modeling approaches and may also be pooled with data from other studies to investigate any association between PF-06801591 exposure and biomarkers or significant safety or efficacy endpoints. The results of these analyses, if performed, may be reported separately.

#### **6.2.5. Biomarker endpoints**

Summary statistics for levels of PD-L1 expression, and number and percentage of participants with tumors categorized with baseline PD-L1 expression level (high vs low) will be presented by arm for Cohort A.

Biomarker data, if available, for Cohort B1 and/or Cohort B2 will be provided in a listing only.

